13.9. Analysis of Secondary Outcomes

Analysis of secondary outcomes will be carried out as follows. For the ED length of stay from ED arrival to discharge, a linear regression analysis similar to the primary outcome will be used to compare the length of stay between the two arms. For the hospital admission rate, chi-square test will be used to compare the admission rates between the two groups. For the count data (e.g., ED re-visits or hospitalizations for VOE within 7 days after the recorded ED visit), it will be first evaluated by collapsing the data into a binary outcome with a cut off at zero and a chi-square test or Fisher exact test (if frequency is below 5 or less) to compare the re-admission rates or rate of a returned ED visit between the two groups. If there is sufficient spread in the count data, a Poisson regression approach will be used to test for protocol differences in the count outcome.

13.10. Analysis of Exploratory Safety Outcomes:

The frequency with which various side effects, adverse event (AE) or serious adverse events (SAE) occur will be carefully tabulated and descriptively summarized. Statistical comparisons of the randomized arms with respect to these events will use chi-square, Fisher exact or other appropriate two-sample methods depending on the nature of the event, interpreting such comparisons in the context of differences between the two randomized arms in the primary and major secondary outcomes and bringing to bear clinical judgment as to the relative seriousness of these side effects and various adverse events.

13.11. Analysis of Subgroups

If the data provide evidence of an overall difference in outcome between the randomized arms, we will examine whether the effect is similar for all patients, or whether it varies according to the pre-specified subgroups. We will also explore if treatment effect differs by enrolling clinical sites. These analyses will utilize the regression models with main effects and interactions between the randomized groups and pre-specified subgroup variables. We recognize that in our study the power of interaction tests is low, especially for the site by treatment interaction. Hence, in addition to the formal assessment of randomized group by covariate interactions, effects of the treatments will be calculated and displayed (with 95% CI) for the pre-specified subgroups of patients. These descriptive summaries will be carefully interpreted in conjunction with the formal interaction tests. The following variable are used to pre-specify subgroups in the subgroup analyses: gender, age (< 30 , ≥ 30 years old), genotypes (Hgb SS, SC, SB+, SB-), route (IV or SC), use (yes/no) of NSAIDS, drug administered, number of repeated doses, and total administrated milligrams of drug. In the R34 study, the IV route was administrated in over 95% of subjects. The subgroup analysis by route will not be carried out if 90% or more subjects receive the IV route.

[figure not shown]

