4. BASIC STUDY DESIGN

A multi-site Phase III, single blinded, RCT will be conducted to address the study aims. The trial will be conducted at six U.S. sites, with an enrollment period of 24 months. Approximately 460 patients will be consented and randomized in order to obtain the study population of 230 patients with at least one ED visit.

The modified intent to treat (ITT) population is adult SCD patients with an ED visit due to VOE. The primary outcome will be change in pain scores from the time of placement in a treatment area to the time of disposition (hospital admission, discharged home or assigned to observation status) or a maximum treatment duration of 6 hours, whichever

comes first. Due to the logistical difficulty in consenting and randomizing patients during an ED visit due to VOE (see Section 7.2), we plan to screen, consent, and randomize patients in a larger population than the target population of adult SCD subjects with ED visits. There is no reason to think the patients randomized are any different from those who eventually do have an ED visit for VOE. The occurrence of VOE is very unpredictable and not related to overall disease severity. Consented adult SCD patients will be randomized to receive analgesic management for VOE via a weight-based SCD analgesic protocol, or via a patient-specific analgesic protocol developed by their hematologist/sickle cell team, which will be used in the patient's future ED visit due to VOE.

Patients will be told what drug and dose they are receiving during their study ED visit, however, they will remain blinded to which analgesic protocol they are randomized. The primary difference between the two analgesic protocols is the starting opioid dose. Other elements of both analgesic protocols reflect the recommendations in the NHLBI expert panel recommendations document, including recommended route and re-dosing intervals. All analgesic protocols, patient-specific and weight-based, will be written by the SCD provider and uploaded to the electronic medical record (EMR) prior to an ED study visit.

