The first choice of opioid (Morphine or hydromorphone) will be based on review of the patient's medical record for pertinent medical history and which drug has been used in the past with greater success. The preliminary calculations above will then be compared to doses of opioids that have been administered to the patient in the ED in the past. If the ED doses and the calculated preliminary doses are within 10% of each other, the preliminary dose will be finalized for that patient's suggested patient-specific analgesic protocol for use at the next ED visit for VOE. If the discrepancy is greater than 10%, the SCD team member will adjudicate this case with the Pain Management Protocols, Clinical Oversight and Implementation Committee to choose a safe dose in the following manner. Whichever of the two doses (preliminary calculations based on home consumption or prior ED doses) is lower will be chosen as the final suggested dose for use at the next ED visit. The lower dose was chosen because it is perceived to be safer. In addition, dose escalation is

permitted at the SCD provider's discretion. For example, if the highest prior ED dose is less than half of the preliminary calculated dose, the highest prior ED dose would be selected and could be increased by 25% for use in the patient-specific analgesic protocol. However, if the previously used ED dose is less than a weight-based dose, a weight-based dose will be used to avoid use of an unreasonably low dose. Per the NHLBI recommendations for the treatment of VOE, the dose frequency for IV pain medication administration will be set at 20-30 minutes unless the SCD provider feels this is not safe.

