8.3 Odd Volume Doses for both analgesic protocols: One barrier to analgesic protocol implementation was the odd doses that resulted in the need to administer a volume of drug less than the amount in which it was supplied. This required “wasting” by the ED nurses and verification by a second nurse. We have consulted with a multidisciplinary team consisting of a pain expert, adult hematologist, and an emergency department physician to determine a strategy to select a final dose that will minimize the need for odd doses and wasting procedures (e.g. morphine 4.3 mg, or hydromorphone 1.3 mg). All doses of morphine can be ordered in increments of 2 mg and doses of hydromorphone can be ordered in increments of 0.5 mg. These doses remain consistent with the patient-specific and weight-based doses with rounding to a safe dose, and will significantly reduce the need to waste drug in most cases. We used this information when creating Table 1. Table 2 describes differences between analgesic protocols in agent, dose, route, monitoring, repeat doses and hydration. The primary difference between analgesic protocols is dose and the provision to increase weight-based doses if insufficient pain relief.

Table 2: Comparison of NHLBI Recommendations: Patient specific vs. Weight-based analgesic Protocol

	Patient-specific analgesic protocol	Weight-based SCD analgesic protocol
Agent	To be determined (TBD) by SCD provider after randomization for use at a future ED visit (morphine sulfate or hydromorphone)	To be determined (TBD) by SCD provider after randomization for use at a future ED visit (morphine sulfate or hydromorphone)
Dose	TBD a priori by SCD provider, based upon current outpatient opioid therapy, if applicable, and past doses required to treat VOE during past ED visits or hospitalizations.	TBD a priori by SCD provider. Initial dose = weight based hydromorphone 0.02 mg/kg morphine sulfate 0.1 mg/kg
Route	Intravenous (IV) unless unable; Sub-cutaneous when IV access is difficult.	Intravenous (IV) unless unable; Sub-cutaneous when IV access is difficult.
Monitoring	Per routine standard of care Q 30 minutes per research protocol / research assistant (sedation level, SpO ₂ , BP, HR, RR).	Per routine standard of care Q 30 minutes per research protocol / research assistant (sedation level, SpO ₂ , BP, HR, RR).

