Repeat doses	TBD by SCD provider – Q 20-30 minutes as required to treat unrelieved pain. No maximum dose set.	Q 20-30 minutes for unrelieved pain. All additional doses, if required, may be provided at the same dose as the 1 st dose, or no more than a one time 25% increase above the original dose.
Intravenous hydration	Maintenance rate (unless dehydrated) when patients are unable to drink fluids adequately.	Maintenance rate (unless dehydrated) when patients are unable to drink fluids adequately.

Once the patient’s analgesic protocol has been developed (patient-specific or weight-based) by the hematologist/sickle cell team, the research team will be notified. The research team will ensure the analgesic protocol is uploaded to the electronic medical record (EMR) within one week of receipt. The analgesic protocol will be available in the EMR for future ED visits.

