 - ii. The patient is admitted to the hospital
 - iii. The patient is assigned to observation status for continued pain management
 - iv. The patient has received 6 hours of treatment

The best approach to missing data is to obtain complete data collection. Age, gender, and SCD type should be available for all patients. SCD type should be one of: Hgb SS, SC, or SB+, SB0 thalassemia. .

The trial will be closely monitored for missing time of bed placement or missing discharge, or 6 hours, pain scores. The first occurrence of missingness within a center will require explanation from the center and a plan to avoid missing data in subsequent patients.

For patients with dosing deviations, we plan to include them in the primary intent-to-treat analysis and collect all study measurements as planned.

Subgroup Analysis of the Primary Endpoint

We will examine whether the finding for the primary endpoint is similar for all patients, or whether it varies according to the following pre-specified subgroups. These will be assessed via interaction terms between treatment and subgroup categories tested at nominal 0.10 level.

- 1) Clinical site
- 2) Gender
- 3) Age (< 30, \geq 30 years old)
- 4) Genotypes (Hgb SS + SB0 and SC + SB+)
- 5) Route (IV or SC) - this will not be carried out if 90% or more subjects receive the IV route.
- 6) Use (yes/no) of NSAIDS
- 7) Drug administered
- 8) Number of repeated doses

9) Total administered milligrams of drug

These analyses will utilize the regression models with main effects and interactions between the randomized groups and pre-specified subgroup variables.

Details of presentation of results are illustrated in section 7.

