7.7. Study Endpoints

7.7.1. Primary Endpoint

As defined in the protocol, the primary endpoint is “change in pain scores from the time of placement in a treatment area to the time of disposition (hospital admission, discharged home, assigned to observation status) or a maximum treatment duration of 6 hours, whichever comes first.” Comparison of mean changes in pain scores and the difference between treatment arms will be done using linear regression, adjusting for the initial pain score at ED arrival, biological variables of SCD genotype, age and gender. Comparison of unadjusted means will also be done using a t-test. P-value, 95% confidence intervals and the mean difference will be displayed in tabular format. The predicted values will be displayed in a scatter plot by treatment.

Descriptive statistics such as n, mean, standard deviation (SD), median, 25th and 75th percentiles will be also presented for the primary endpoint.

For subgroup analysis of the primary endpoint, in addition to the formal assessment of randomized group by covariate interactions as described in section 4, effects of the treatments will be calculated and displayed (with 95% CI and p-values) for the pre-specified subgroups of patients in both tabular and graphic format. These descriptive summaries will be carefully interpreted in conjunction with the formal interaction tests.

Please refer to section 4 for methods of analysis.

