17.3. Subgroup Analysis of the Primary Endpoint

	Treatment A N=	Treatment B N=	Estimate (95% CIs), SD	P-value
Gender				
Male				
Female				
Age				
< 30				
≥30				
Genotypes				
SS + SB-				
SC + SB+				
Route				
IV				
SC				
NSAID				
Yes				
No				
Drug Administered				
Yes				
No				
Number of Repeated Doses				
Total Administered Milligrams of Drug

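### Number of repeated doses and total milligrams given are used as treatment-effect subgroups although both arise after randomization, so their strata are not randomized comparisons

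*Protocol*

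**What the plan says.** Protocol 13.11 lists the variables that define subgroups of the primary endpoint, ending with "number of repeated doses, and total administrated milligrams of drug". It plans regression models with treatment-by-subgroup interactions and treatment effects with 95% CIs inside each subgroup. It does this only if there is evidence of an overall difference.

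SAP 4.1 repeats both variables as items 8 and 9: "These will be assessed via interaction terms between treatment and subgroup categories tested at nominal 0.10 level". SAP 7.7.1 adds that "effects of the treatments will be calculated and displayed (with 95% CI and p-values) for the pre-specified subgroups of patients". Table 17.3 has a row for each, the last being "Total Administered Milligrams of Drug". No cut-points are given for either.

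On how dose arises:

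- Protocol 4: "The primary difference between the two analgesic protocols is the starting opioid dose".
- Protocol 8.3: "The primary difference between analgesic protocols is dose and the provision to increase weight-based doses if insufficient pain relief".
- Protocol 8.2.1, for a low prior ED dose in the patient-specific arm: "a weight-based dose will be used to avoid use of an unreasonably low dose".
- Protocol Table 2, repeat doses in the patient-specific arm: "as required to treat unrelieved pain. No maximum dose set". In the weight-based arm repeats are also for unrelieved pain, but at the first dose or with a single increase of at most 25%.

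The primary endpoint (Protocol 11) runs from treatment-area placement to disposition or 6 hours, so these doses are given while the outcome is developing. SAP 7.5 separately plans descriptive statistics for cumulative morphine-equivalent dose.

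**The concern.** A treatment-effect subgroup answers whether the randomized contrast differs between kinds of patient. That needs a grouping variable which the assigned treatment does not influence. Total milligrams is largely a product of the assignment, and the number of repeats is a response to how the pain is going. Conditioning on either one compares patients who reached the same stratum by different routes in the two arms.

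At stake is the reading of the subgroup table. An effect that is the same in every patient can appear larger or smaller inside dose strata, and for milligrams it can appear to vary between them. SAP 5 says that the final report will be used for publication, so such effects, with p-values, could be read as showing who should receive a patient-specific protocol.

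**Working it through.** **1. The plan's own figure.** 230 × 0.90 / 2 = 103.5 analysed per arm. Power = Φ(14/31 × √(103.5/2) − 1.96) = Φ(3.25 − 1.96) = Φ(1.29) ≈ 90.1%, against the stated 90%. Nothing in this point changes it.

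**2. Why equal milligrams do not mean comparable patients.** Total = dose per administration × number of administrations. Take the 8 mg morphine dose that Protocol Table 1 gives for 70–89.9 kg and, as an assumption, a patient-specific dose 1.5 times as large. A weight-based total of 3 × 8 = 24 mg matches a patient-specific total of 2 × 12 = 24 mg. The weight-based patient still had unrelieved pain one administration later. The pairing reflects arm and response together.

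**3. Raw milligrams sort by drug.** For the same weight, Table 1 gives 8 mg morphine or 1.5 mg hydromorphone. Three administrations give 24 mg or 4.5 mg. At the 5:1 conversion in Protocol 8.2.2, 4.5 × 5 = 22.5 mg morphine equivalent, so nearly equal exposures fall at opposite ends of the raw scale.

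**4. Illustration of size.** Inputs from the documents: weight-based mean reduction 29 mm (Protocol Table 3), SD 31 and effect 14 mm (Protocol 13.7), 8 mg dose (Table 1). Assumed: correlation ρ between number of doses and pain reduction of −0.3 or −0.5; dose ratio between arms 1.0 to 2.0; median split.

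Formulas: Y = 29 + 14A + 31e. L = ρ(Y − 29)/31 + √(1 − ρ²)·z. Number of doses = 4 + 1.5L, rounded and kept within 1 to 12. Milligrams = number × 8 × (ratio if patient-specific). Here e and z are independent standard normal variables, and A is 1 for patient-specific. Every patient has the same 14 mm effect.

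| Stratifier, all on one drug | ρ = −0.3, low/high half | ρ = −0.5, low/high half |
|---|---|---|
| Number of doses (ratio 1.0) | 13.3 / 13.0 mm | 12.2 / 11.3 mm |
| Milligrams, ratio 1.0 | 13.3 / 13.0 mm | 12.2 / 11.3 mm |
| Milligrams, ratio 1.25 | 17.1 / 17.1 mm | 18.2 / 18.6 mm |
| Milligrams, ratio 1.5 | 17.1 / 17.3 mm | 18.2 / 18.4 mm |
| Milligrams, ratio 2.0 | 24.5 / 25.1 mm | 30.4 / 31.8 mm |

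The dose-count row hardly changes at the other ratios. For number of doses the distortion is 14 − 13.3 = 0.7 mm to 14 − 11.3 = 2.7 mm. For milligrams it runs from 0.7 mm at ratio 1.0 to 31.8 − 14 = 17.8 mm at ratio 2.0. With half of each arm on hydromorphone and milligrams left raw, the halves show about 11 to 17 mm.

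**5. With no true effect.** Dose-count strata show no bias, and neither do milligram strata at ratio 1.0. At ratios 1.25 to 2.0, with one drug, milligram strata show a false advantage of about 4 to 23 mm. At ratio 2.0, 16–37% of patient-specific and 84–95% of weight-based patients fall in the low-milligram half. Counts are discrete, so the median often falls on a tie and single results can move by several mm between runs.

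**6. Direction.** In a different assumed model, linear in dose and severity, milligram strata show 16.0 to 21.9 mm if the severity–outcome correlation is −0.5, but 7.2 to 13.2 mm if it is +0.5. These are averages over trials with overall p ≤ 0.05, where the overall estimate averages 14.5 to 14.7 mm. The sign therefore depends on inputs that the documents do not give.

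**The case against.** The strongest reply is that these are exploratory displays, already hedged. Protocol 13.11 admits low interaction power and runs subgroups only after an overall difference. Both it and SAP 7.7.1 call the within-subgroup results descriptive and ask for careful interpretation. This stands, and it limits the harm. In assumed models with a true effect of zero, the Protocol's condition keeps the share of trials in which a half reaches p < 0.05 at 2–5%, against 2.5–2.6% for a split fixed before randomization. But SAP 4.1 does not repeat that condition. The condition also admits exactly the case in step 4, where the arms differ and the strata misstate by how much. Careful reading cannot restore a comparison that conditioning has removed.

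A second reply is that the interaction test may be barely disturbed. For repeats this is fair: under assumed models with a constant effect it rejects in 9–13% of trials, close to its nominal 10%. The problem there is the size of the within-stratum effects rather than a spurious interaction.

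A third is covariate adjustment. The primary model uses initial pain, genotype, age and gender; whether the subgroup models do so is not stated. These covariates precede dosing and need not capture pain during the visit, which drives repeats. SAP 7.5 notes that the CRF lacks some of what guides later dosing. That remark concerns adherence, but I infer that the same gap limits adjustment.

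**Conclusion.** The concern holds for these two variables on the documents' own description of dosing, without any simulation. Strata of repeat count or total milligrams are not randomized comparisons, and the raw milligram scale adds a sorting by drug. The assumed models put the distortion at a few mm for repeats and from negligible to more than 10 mm for milligrams, depending mainly on the dose ratio between arms and the drug mix. The documents give neither, nor any cut-points, so no single figure should be cited as expected.

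A reader might infer three stronger things that the documents do not support:

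- That the trial's main result is compromised. It is not: the primary analysis, power and futility rule do not use these variables.
- That the strata will exaggerate the patient-specific benefit. The direction is not determined. Wider ranges for repeats can be produced only by assuming further effects of arm on repeat count, or other dosing behaviour, which the documents do not quantify.
- That every subgroup variable recorded after randomization is invalid. A later value unaffected by assignment can define a valid subgroup. Nothing ties IV access to arm, and the route analysis is already dropped if 90% or more receive IV; Protocol 13.11 reports over 95% in the R34 study.

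**What to change.** - Remove number of repeated doses and total administered milligrams from the subgroup and interaction lists in Protocol 13.11 and SAP 4.1, and from SAP table 17.3.
- Report both descriptively by arm in SAP 7.5, with dose in morphine equivalents as already planned there and the number of repeat doses added.
- Protocol Table 2 has the agent chosen after randomization. Label the drug-administered subgroup as defined after randomization and not a randomized subgroup comparison, or report it by arm.
- Define NSAID use as home use before the ED visit (SAP table 13.1), if that is the recorded variable. Otherwise label it in the same way.
- Leave route under its existing 90% rule.

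The cost is text edits. The schedule of assessments already records drug, dose and timing, so the dose summaries need no new data. Two exploratory displays are lost.

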13.12. Analysis of Planned Interim Monitoring

For ethical reasons, an interim examination of key safety data will be performed at regular intervals during the course of the trial. In addition, the interim monitoring will also involve a review of the SD of the primary outcome for a blinded sample size re-estimation; as well as patient recruitment, compliance with the study protocol, status of data collection, and other factors which reflect the overall progress and integrity of the study. The interim results will be carefully and confidentially reviewed by the DSMB. No

efficacy analysis is planned in this trial unless it is requested by the DSMB and after careful discussion with the Executive Committee. Two interim analyses for futility using conditional power approach will be conducted when approximately one-third ($N \sim 77$ patients with ED visits) and two-thirds ($N \sim 154$ patients with ED visits) of the total 230 patients in the modified ITT population have completed the ED visits with measurements on the primary outcome. This timeline can be altered based on the input from the DSMB. The goal of the interim analysis is to determine whether to stop the trial early because it is unlikely to show superiority. If the conditional power falls below 10% then the DSMB may consider recommending to stop the trial due to futility. To reduce the likelihood of an underpowered study due to incorrect sample size assumptions, a blinded sample size re-estimation will be conducted at the time of the two planned futility analyses. The sample size re-estimation plan is for the sole purpose of avoiding an underpowered trial due to a higher SD of pain score reduction or higher missing data rate than assumed. It is not for interim testing of a treatment effect. The two interim analyses for futility and the blinded sample size re-estimations will be carried out by the senior statistician under the supervision of [name]. [name] will be blinded to the observed trend of treatment effect and will present the conditional powers under different scenarios of treatment trend for the remaining subjects to the DSMB. Even if the formal futility interim analyses are presented to the DSMB, the DSMB will consider all the relevant issues related to a potential decision to stop the trial and most likely will not base such a decision entirely on the statistical arguments.

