13. STATISTICAL CONSIDERATIONS

13.6. Overview

Detailed description of the plan for statistical analysis of each endpoint will be detailed in a Statistical Analysis Plan (SAP) that will be prepared after the final study protocol is approved. The SAP will be prepared by the DCC senior statistician under [name] supervision.

Descriptive statistics will be used to summarize patient socio-demographic and clinical characteristics. The analyses of primary and secondary outcomes as well as the summary description of pain-related side effects and safety will be carried out by the DCC statistical service. Means, standard deviations, medians, 25th and 75th percentiles, minimum and maximum will be presented for continuous variables; the number and frequency of patients in each category will be presented for nominal variables. For all analyses, a two-sided p-value ≤ 0.05 will be considered statistically significant. Analyses will be performed using SAS version 9.4 or higher software (SAS Institute, Inc., Cary, NC).

Multiple Comparisons: With the pre-specified primary and secondary analyses, we

recognize that there is a multiplicity of analyses to be performed, which leads to an increased probability that at least one of the comparisons could be "significant" by chance. There are adjustments (e.g., based on the Bonferroni inequality) that can be used to preserve the overall type I error level. To attempt to adjust for the effects of the repeated significance testing that will occur as part of potential interim monitoring (discussed below), plus to adjust for the multiplicity of secondary outcomes, would require that very small significance levels be used for every comparison. Rather than taking this approach we will be conservative in the interpretation of secondary analyses, taking into account the degree of significance, and looking for consistency across outcomes. The actual p-value for each comparison will be reported to aid in the overall interpretation. In addition to the pre-specified primary outcome, we will use pre-specified secondary outcomes and pre-specified subgroups to help avoid over-interpretation and to help guard against and reduce the problems inherent with multiple testing.

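### If the DSMB asks for an efficacy look, no boundary is set and the protocol declines to adjust for repeated testing: at 0.05 per look, overall type I error would be about 8–9% with one look and 10.7% with two

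*Protocol*

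**What the plan says.** **Interim monitoring (protocol 13.12).** The planned looks concern futility: "Two interim analyses for futility using conditional power approach will be conducted when approximately one-third" and two-thirds (about 77 and 154) "of the total 230 patients in the modified ITT population have completed the ED visits with measurements on the primary outcome". The DSMB may consider stopping if conditional power is below 10%, and it can change the timing. Sample size re-estimation is blinded and is expressly not a test of the treatment effect. On efficacy, the section says that no "efficacy analysis is planned in this trial unless it is requested by the DSMB and after careful discussion with the Executive Committee". The "no" that opens that sentence matters: the default is no look, with an exception on request. The exception comes without a number of looks, a timing, a boundary or a spending function.

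**Significance level and multiplicity (protocol 13.6).** The general rule is: "For all analyses, a two-sided p-value ≤ 0.05 will be considered statistically significant". The paragraph on multiple comparisons names the "repeated significance testing that will occur as part of potential interim monitoring" and says that adjusting for this together with the secondary outcomes "would require that very small significance levels be used for every comparison". It continues: "Rather than taking this approach we will be conservative in the interpretation of secondary analyses".

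**SAP.** Section 4.1 defines one hypothesis test of the primary endpoint, at the final analysis. Section 5 says that interim calculations will be carried into the final analysis. No boundary or alpha-spending rule appears anywhere in the SAP.

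**DSMB charter (protocol 14.11).** The charter is cited for the composition of the board, not for a stopping boundary.

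**The concern.** Sections 13.6 and 13.12 fit together badly. One opens the door to an efficacy test on accumulating data. The other names that source of repeated testing, gives a reason for not correcting for it, and sets a single 0.05 threshold for everything. The substitute for a correction is cautious reading of secondary analyses, which does nothing for the primary endpoint. If an efficacy look took place, the primary hypothesis would have no stated protection.

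The likely trigger adds to the problem. The DSMB receives conditional power at one-third and two-thirds of the patients, and those figures depend on the accumulating outcome data. A request for an efficacy analysis could therefore follow from what the board has seen. The request is then discussed with the Executive Committee, which consists of trial leadership (protocol 14.7). A threshold agreed at that stage cannot be relied on to be independent of the data. At stake is the 0.05 type I error on which protocol 13.7 and SAP 2.4 base the sample size.

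**Working it through.** **Inputs.** Two-sided alpha 0.05 (protocol 13.6). N = 230, difference 14 mm, SD 31 mm, 10% missing (13.7). 1:1 allocation (8.2). Interim times 77 and 154 of 230 (13.12), so the information fractions are 77/230 = 0.335 and 154/230 = 0.670. *Assumptions, not in the documents:* how many efficacy looks are taken and when, and that p ≤ 0.05 at any of them would count as success.

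**Step 1: the plan's own power figure.** Evaluable patients per arm: 230 × 0.90 / 2 = 103.5. Standardised effect: 14 / (31 × √(2/103.5)) = 3.249. Power ≈ Φ(3.249 − 1.960) = Φ(1.289) = 90.1% (89.9% with the noncentral t). The stated 90% is reproduced.

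**Step 2: overall type I error at 0.05 per look.** Under the null, the sequential z-statistics are jointly normal with correlation √(tᵢ/tⱼ) for tᵢ < tⱼ. The overall two-sided error is 1 − P(|Z₁| < 1.96, …, |Z_K| < 1.96). The correlations are √(1/3) = 0.577 between one-third and final, √(2/3) = 0.816 between two-thirds and final, and √(1/2) = 0.707 between the two interim looks.

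| Efficacy tests, each at 0.05 | Overall type I error |
|---|---|
| Final only (the default plan) | 5.0% |
| One look at two-thirds, plus final | 7.7% |
| One look at one-half, plus final | 8.3% |
| One look at one-third, plus final | 8.8% |
| Looks at 77 and 154, plus final | 10.7% |

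Two million simulated trials for the last row also gave 10.7%. Whatever its timing, a single look stays below 1 − 0.95² = 9.75%, the value for independent tests. The 10.7% is not a ceiling: three interim looks plus the final, equally spaced, would give 12.6%.

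**Step 3: what a pre-set boundary would cost.**

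- *Interim two-sided p < 0.001, final at 0.05.* Overall error is 5.05% with a look at one-third, 5.01% with a look at two-thirds, and 5.05% with both. The final level and fixed-sample power do not change.
- *Lan-DeMets spending of O'Brien-Fleming type,* α(t) = 4[1 − Φ(z₀.₉₈₇₅/√t)], at 77, 154 and 230. The nominal two-sided levels are 0.0002, 0.0122 and 0.0462, and the overall error is 5.0%. Fixed-sample power at the final level is Φ(3.249 − 1.994) = Φ(1.255) ≈ 89.5%.
- *The same interim boundaries, but the final test left at 0.05.* Overall error is 5.4%, so the spending option needs the lower final level.

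For the primary endpoint, then, the reason given in 13.6 for not adjusting does not apply: the final test need not move to a very small level.

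**The case against.** The strongest reply is that nothing is wrong with the plan as it will normally run. No efficacy look is planned, the two scheduled looks serve futility only, the futility rule is non-binding and so cannot raise type I error, and the re-estimation is blinded. All of that stands, and it makes the point conditional.

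A reader might infer that the final 0.05 test itself has about 11% error. It does not. Taken alone it has 5%, and the inflation belongs to the sequence of tests. Nor does 10.7% follow from a single look; it needs two.

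A reader might also infer that one efficacy look is enough to break the 0.05 claim. The documents do not support that. Error rises only if crossing the threshold at that look counts as success, and no efficacy stopping rule is written down. A strict threshold would leave the error near 5%.

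It can further be said that 13.6 rejects only a joint correction for interim monitoring and secondary outcomes, and never states that a requested primary look would be tested at 0.05. It is true that this has to be inferred. But the paragraph names interim testing among the things left unadjusted, the 0.05 rule covers all analyses, and no other threshold exists in either document. As written, 0.05 is the only level available.

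Finally, a boundary could be agreed between the request and the look, so it would be too strong to say that a late boundary can never repair the problem. Still, the DSMB may by then have seen conditional power, and independence from the data could not be shown. A boundary in the charter, which is not among the documents, would conflict with 13.6 as it reads now.

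**Conclusion.** The point holds in conditional form. Without an efficacy look, type I error is 5%. With a look requested under 13.12, the primary endpoint has no specified boundary, and the only stated level is 0.05. Testing at that level gives an overall error of 7.7% to 8.8% for one look at either planned interim time, and 10.7% for looks at both. These figures rest on the assumed number and timing of looks and on an interim p ≤ 0.05 counting as success. They are scenarios, neither expected values nor a maximum. This is more than a missing detail, because 13.6 considers the adjustment and declines it. It should be corrected because the remedy is cheap and it protects the trial's one confirmatory claim.

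**What to change.** 1. In protocol 13.12 and in the SAP, choose one of the following now:
   - any DSMB-requested efficacy look uses two-sided p < 0.001, with the final test at 0.05; or
   - any such look uses Lan-DeMets spending of O'Brien-Fleming type, with the final level adjusted to match (about 0.046 for looks at 77 and 154); or
   - no efficacy look will be done.
2. In protocol 13.6, exempt interim testing of the primary endpoint from the no-adjustment paragraph, so that the paragraph covers secondary outcomes only, and make the general 0.05 rule subject to the chosen boundary.
3. Make sure that the DSMB charter carries the same rule.

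**Cost.** A few sentences. A requested look could then support efficacy only on strong evidence. Under the first option, overall error is about 5.05% rather than exactly 5%. Under the spending option, the final level drops to about 0.046 and fixed-sample power from about 90% to about 89.5%. Under the third option, the DSMB gives up the possibility of an efficacy look.
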